7.2.2.2. DLT-Equivalent Toxicities

A DLT-equivalent toxicity is any event listed in [Table JZDA.7.2](#) occurring after Cycle 1 in Phase 1a or in any cycle of Phase 1b that would have met criteria for DLT if it had occurred during the DLT observation period. For individual patients experiencing a DLT-equivalent toxicity, dose modifications will be made as outlined in Section [7.4](#).

7.2.2.3. Recommended Phase 2 Dose Determination

The RP2D will be chosen following discussion between the Lilly CRP/CRS and the investigators based on consideration of the totality of the data, including but not limited to LY3415244 dose adjustments (delays, reductions, or omissions), AEs, chronic intolerance, PK and pharmacodynamic data, and irAEs. The final RP2D to be carried forward into any future studies will be confirmed or changed based on the combined data from Phase 1a and Phase 1b.

7.3. Blinding

This is an open-label study.

7.4. Dose Modification

No dose modification is allowed during Phase 1a DLT observation period (Cycle 1).

After the Phase 1a DLT observation period (Cycle 1), doses of the study drug may be delayed or discontinued to manage specific AEs or other toxicities. Dose reductions are not permitted. All dose modifications should be documented, including the approach taken and a clear rationale for the need for modification.

The investigator must assess whether the toxicity is at least possibly due to study treatment and apply the dose-modification guidelines. Investigators are encouraged to consult Lilly for additional guidance.

If a patient requires a dose delay, study treatment should be resumed within 1 cycle, if possible and appropriate. If study treatment cannot be resumed within 1 cycle, every effort should be made to restart on the first day of the next cycle. In rare circumstances, a delay of >28 days may be permitted before permanent treatment discontinuation, as long as the patient demonstrates clinical benefit, does not have objective progression, and is recovering from the toxicity. Such circumstances must be discussed with the Lilly CRP/CRS.

Adverse events of immune-related etiology are expected because of the study drug's mechanism of action and may occur shortly after the first dose or several months after the last dose. Study treatment must be withheld if the patient experiences a drug-related toxicity or a severe or life-threatening AE. Dose reductions are not permitted.

A 4-hour observation period is required after the administration of LY3415244 in Cycles 1 to 3. During observation period, patients treated with LY3415244 should be closely monitored for signs and symptoms indicative of an infusion-related reaction by medical staff from the start of the infusion until 4 hours after the end of the infusion, in an area where emergency medical resuscitation equipment and other agents (epinephrine prednisolone equivalents, etc.) are available. LY3415244 infusion-related reactions will be defined according to the Common Terminology Criteria for Adverse Events (CTCAE), Version 4.0 definition of IRRs.

Table JZDA.7.3 presents instructions for management of infusion-related reactions associated with LY3415244.

Table JZDA.7.3. Management of Infusion-Related Reactions

Grade	Management
2	First occurrence
	
Stop the infusion and proceed with following:
 
 1. If resolved to Grade 0 or 1 within 1 hour after stopping the infusion 
 a. restart the infusion at 50% of the original rate (for example, reduce from 100 to 50 mL/hr) 2. If NOT resolved to Grade 0 or 1 within 1 hour after stopping the infusion: 
 a. delay study treatment until the symptoms resolve in \leq48 hours, and b. premedicate prior to the next scheduled dose. Premedication should be administered 1.5 hours (\pm30 minutes) prior to the LY3415244 infusion with diphenhydramine (or other antihistamine), acetaminophen (or other antipyretic), steroids etc., at the discretion of treating physician.
3 or 4	
Second occurrence
 
Immediately and permanently discontinue study treatment
 
Immediately and permanently discontinue study treatment.
 
Patients who experience a Grade 3 IRR that resolves within 6 hours may continue on study treatment. For subsequent infusions, the patient should be premedicated 1.5 hours (\pm30 minutes) prior to the LY3415244 infusion with diphenhydramine (or other antihistamine), acetaminophen (or other antipyretic), steroids etc., at the discretion of treating physician.
 
If symptoms reappear, immediately and permanently discontinue study treatment.

Table JZDA.7.4 presents guidance for irAE management (including use of corticosteroids) and criteria for dose delays and discontinuations if the patient experiences a potential irAE considered at least possibly related to LY3415244.

Because of the potential for rapid and serious sequelae associated with irAEs, early intervention with corticosteroids is encouraged, concurrent with further diagnostic medical evaluations for possible nonimmune-related causes of AEs. The treatment plan should always include a thorough workup of the issue to rule out other potential etiologies such as infection. Guidelines used by local standards such as, but not limited to Haanen and colleagues (2017), Puzanov and colleagues (2017), or Brahmer and colleagues (2018), supersede the guidelines provided in Table JZDA.7.4 if deemed appropriate by the investigator. If a patient experiences an irAE that is not listed in this table, consult the Lilly CRP/CRS to discuss appropriate management.

Other corticosteroid options can be given at equivalent doses. Corticosteroids should be tapered over 1 month once symptoms improve to Grade \leq 1, and study treatment should not be restarted until corticosteroid tapering is complete. During corticosteroid use, use prophylactic antibiotics to prevent opportunistic infections.

Table JZDA.7.4. Dose Modification Guidelines and AE Management for Toxicities At Least Possibly Related to Study Drug

SOC	Toxicity	CTCAE Grade and/or Symptoms ^a		Treatment Plan ^b
		Grade	Symptoms	
Endocrine	Thyroid issues		If symptomatic	
 Start thyroid replacement therapy and/or medical management and continue study treatment For Grade 3 hyperthyroidism, withhold study treatment until hyperthyroidism improves to Grade ≤ 1 For Grade 4 hyperthyroidism, discontinue study treatment
Endocrine	Hypotension, altered mental status, headache, fatigue, hyperglycemia		For endocrine issues other than thyroid issues (for example, hypophysitis, diabetes mellitus-type 1)	
 Withhold study treatment and administer prednisone 1-2 mg/kg/day Resume study treatment when symptoms resolve and the patient is stable on hormone replacement therapy For Grade 3 or 4, discontinue study treatment For severe adrenal crisis, give stress dose of IV corticosteroids with mineralocorticosteroid

Dose Modification Guidelines and AE Management for Toxicities At Least Possibly Related to Study Drug

SOC	Toxicity	CTCAE Grade and/or Symptoms ^a		Treatment Plan ^b
		Grade	Symptoms	
Gastrointestinal	Diarrhea, Abdominal pain, Blood in stool, Colitis	2		
 Withhold study treatment, give antidiarrheal medication, and check etiology If the event continues for >5 days despite the use of antidiarrheal medications, start prednisone 0.5-1 mg/kg/day Resume study treatment after the event resolves to Grade ≤ 1
	Diarrhea, Ileus, Perforation, Colitis	≥ 3		
 Withhold study treatment and administer prednisone 1-2 mg/kg/day (no corticosteroids if possible perforation) If the event persists >3 days despite use of corticosteroids, add a nonsteroidal immunosuppressive agent and discontinue study treatment.^c Resume study treatment after the event resolves to Grade ≤ 1 Discontinue study treatment if Grade 3 persists For Grade 4, discontinue study treatment
	Pancreatitis	1-2	Increase in amylase and lipase	
 Withhold study treatment and administer prednisone 0.5-1 mg/kg/day Resume study treatment after the event resolves to Grade ≤ 1
		≥ 3		
 Discontinue study treatment and administer prednisone 1-2 mg/kg/day^d

Dose Modification Guidelines and AE Management for Toxicities At Least Possibly Related to Study Drug

SOC	Toxicity	CTCAE Grade and/or Symptoms ^a		Treatment Plan ^b
		Grade	Symptoms	
Hepatobiliary	Transaminitis, elevated bilirubin	2	
 AST or ALT between $3 \times$ ULN and $5 \times$ ULN, or TB between $1.5 \times$ ULN and $3 \times$ ULN 	
 Withhold study treatment and administer prednisone 1-2 mg/kg/day Resume study treatment after symptoms resolve to Grade ≤ 1
		≥ 3	
 AST or ALT $>5 \times$ ULN, or TB $>3 \times$ ULN 	
 Discontinue study treatment and administer IV methylprednisolone 2-4 mg/kg/day If the event continues for >3 days despite corticosteroids, add a nonsteroidal immunosuppressive agent^c
Nervous system	Weakness, paresthesia (for example, Guillain-Barre syndrome or myasthenia gravis)		Moderate symptoms with no impact on ADL	Withhold study treatment until symptoms resolve
		≥ 2 irAE	Impact on ADL	Discontinue study treatment. Give appropriate medical intervention and prednisone 1-2 mg/kg/day
Respiratory	Dyspnea, hypoxia, pneumonitis	1		Consider withholding study treatment until the patient is stable
		2	Mild to moderate symptoms	
 Withhold study treatment and administer prednisone 1-2 mg/kg/day Resume study treatment after the event resolves to Grade ≤ 1
		≥ 3	Severe	
 Discontinue study treatment and administer: 
 IV methylprednisolone 2-4 mg/kg/day and prophylactic antibiotics If the event remains at Grade ≥ 3 for >2 days despite corticosteroids, add a nonsteroidal immunosuppressive agent^c

Dose Modification Guidelines and AE Management for Toxicities At Least Possibly Related to Study Drug

SOC	Toxicity	CTCAE Grade and/or Symptoms ^a		Treatment Plan ^b
		Grade	Symptoms	
Cardiac	Myocarditis, cardiac function abnormalities (for example, dysrhythmia, valvular abnormalities)	≥1		
 Discontinue study treatment and administer 
 IV methylprednisolone 2-4 mg/kg/day Consider immunosuppressives without immediate response to steroids (for example, mycophenolate, infliximab, or anti-thymocyte globulin) Consult with cardiology immediately and Lilly CRP/CRS; if available, transfer to cardiac care unit
Renal and urinary	Elevated creatinine, decreased urine output, blood in urine, edema, nephritis	1	<1.5 x baseline	Continue study treatment
		2-3	1.5 × ULN < × ≤ 6 × ULN or >1.5 × baseline	
 Withhold study treatment and administer prednisone 0.5-1 mg/kg/day Resume study treatment after the event resolves to Grade ≤1 If elevations persist for >7 days or worsen, follow the guidelines for a Grade 4 event
		4	>6 × ULN	Discontinue study treatment and administer prednisone 1-2 mg/kg/day

Dose Modification Guidelines and AE Management for Toxicities At Least Possibly Related to Study Drug

SOC	Toxicity	CTCAE Grade and/or Symptoms ^a		Treatment Plan ^b
		Grade	Symptoms	
Skin	Rash, pruritus		Moderate rash (diffuse, ≤30% BSA)	
 Withhold study treatment For rash on <10% of the patient's BSA, administer intermediate or high-potency topical corticosteroid For rash on 10%-30% of the patient's BSA, administer systemic corticosteroids Resume study treatment if the rash improves to mild (localized) and the corticosteroid dose is <7.5 mg/day
	Stevens–Johnson syndrome, toxic epidermal necrolysis, necrosis, bullous or hemorrhagic lesions			Discontinue study treatment and administer prednisone 1-2 mg/kg/day
Ophthalmological	Eye disorders (for example, uveitis, episcleritis)	≥2		
 If mild, consider topical steroids (for example, 1% prednisolone); otherwise, discontinue study treatment and administer 
 Oral or IV methylprednisolone 2-4 mg/kg/day Consult ophthalmologist and Lilly CRP/CRS.

Dose Modification Guidelines and AE Management for Toxicities At Least Possibly Related to Study Drug

Abbreviations: ADL = activities of daily living; ALT = alanine aminotransferase; AST = aspartate aminotransferase; BSA = body surface area; CRP = clinical research physician; CRS = Clinical Research Scientist;

CTCAE = Common Terminology Criteria for Adverse Events, Version 4.0; irAE = immune-related adverse event; IV = intravenous; SOC = system organ class; TB = total bilirubin; ULN = upper limit of normal.

- a If symptoms of grade is not specified, use CTCAE Version 4 definitions; otherwise, use the definitions provided in this table.
- b Discontinuation of study treatment is permanent; resumption of study treatment is not allowed. If a toxicity does not resolve to Grade 0-1 or if the corticosteroid dose cannot be reduced to ≤ 10 mg/day of prednisone or equivalent within 12 weeks, consult with the Lilly CRP/CRS about discontinuing study treatment.
- c Immunosuppressive refers to infliximab or cyclophosphamide.
- d Patients who have asymptomatic or clinically non-significant Grade 3 or 4 lipase or amylase elevations (for example, not associated with clinical symptoms or radiological signs of pancreatitis) that are transient as demonstrated by a decrease of at least 1 CTCAE Grade within 7 days (± 3 days) of onset will not require discontinuation of LY3415244. If the elevation does not decrease by at least 1 CTCAE Grade within this time window, LY3415244 treatment may continue only after consultation and discussion with the Lilly CRP/CRS.

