7.1. Treatment Administered

LY3415244 will be administered as an IV infusion over approximately 60 minutes, depending on dose level (doses \leq 70 mg may require bolus IV infusion). In Cycles 1 through 3, the LY3415244 infusion will be followed by a 4-hour observation period.

Table JZDA.7.1 shows the treatment regimen.

Table JZDA.7.1. Treatment Regimen

	Cohort	Dose of LY3415244	Route	Dosing Schedule
Phase 1a: Dose Escalation	A1	3 mg	IV	D1 and D15 of each 28-day cycle (Q2W)
	A2	10 mg		
	A3	30 mg		
	A4	70 mg		
	A5	200 mg		
	A6	600 mg		
	A7	1000 mg		
	A8	Optional: TBD ^a		
Phase 1b: Dose Expansion	B	RP2D	IV	D1 and D15 of each 28-day cycle (Q2W)
	C			
	D			
	E			

Abbreviations: C = cycle; D = day; IV = intravenously; mg = milligrams; Q2W = every 2 weeks; RP2D = recommended Phase 2 dose; TBD = to be determined.

^a Enrollment of Cohort A8 is optional. It will be initiated if Cohort A7 is tolerated and PK/PD analyses suggest that another dose may be appropriate. The dose will not exceed 1500 mg.

The investigator or his/her designee is responsible for the following:

- explaining the correct use of the drug(s) and the planned duration of each individual's treatment to the patient and study site personnel
- verifying that instructions are followed properly
- maintaining accurate records of study drug dispensing and collection
- at the end of the study returning all unused medications to Lilly, or its designee, unless Lilly and sites have agreed all unused medications are to be destroyed by the site, as allowed by local law

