8.1. Discontinuation from Study Treatment

Patients will be discontinued from study treatment in the following circumstances:

- the patient is enrolled in any other clinical study involving an investigational product or any other type of medical research judged not to be scientifically or medically compatible with this study.
- the patient becomes pregnant during the study
- the patient is significantly noncompliant with study procedures and/or treatment as described in Section 7.6
- The patient experiences a DLT (see Section 7.2.2.2) during Cycle 1, a DLT-equivalent toxicity (see Section 7.2.2.2.2), or other unacceptable toxicity
- the patient requires a dose delay of >28 days, except as described in Section 7.4
- the patient, for any reason, requires treatment with another therapeutic agent that has been demonstrated to be effective for treatment of the study indication.
Discontinuation from study treatment will occur prior to introduction of the new agent
- the investigator decides that the patient should be discontinued from study treatment
- the patient requests to be discontinued from study treatment
- the patient has received the maximum duration of 12 months of study treatment (longer duration may be considered for a patient receiving clinical benefit, in consultation with the Lilly CRP/CRS). If tumor imaging shows initial disease progression, at the discretion of treating physician, patients may remain on study treatment with repeat imaging 4 to 6 weeks later to assess tumor response or confirm progression per RECIST 1.1 with confirmatory scan on disease progression

Patients who are discontinued from study treatment will have follow-up procedures performed as shown in the Schedule of Activities (Section 2).

Discontinuation of study treatment may be considered for patients who meet all of the following criteria:

- have a confirmed CR, **and**
- have received study treatment for at least 24 weeks, **and**
- have received at least 2 cycles of study treatment beyond the date when the initial CR was declared.

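### Protocol Section 7.4's steroid-taper sentence contradicts the restart rules in Table JZDA.7.4 and uses most or all of the 28-day delay limit, and the start of a delay is not defined

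*Protocol*

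**What the plan says.** Five places in the protocol govern restart after an immune-related adverse event (irAE) treated with corticosteroid.

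- **Section 7.4, text before Table JZDA.7.4.** "Corticosteroids should be tapered over 1 month once symptoms improve to Grade" ≤1, and "study treatment should not be restarted until corticosteroid tapering is complete".
- **Section 7.4, general delay rule.** After a delay, "study treatment should be resumed within 1 cycle, if possible and appropriate"; failing that, "every effort should be made to restart on the first day of the next cycle". Then: "In rare circumstances, a delay of >28 days may be permitted before permanent treatment discontinuation". For this the patient must be benefiting, free of objective progression and recovering, and the case must be discussed with the sponsor's physician.
- **Section 8.1.** Treatment is discontinued if "the patient requires a dose delay of >28 days, except as described in Section 7.4".
- **Table JZDA.7.4, resume rows.** Six rows that use systemic steroid (gastrointestinal Grade 2 and Grade ≥3, pancreatitis Grade 1-2, hepatobiliary Grade 2, respiratory Grade 2, renal Grade 2-3) resume at Grade ≤1 and do not mention the taper. The non-thyroid endocrine row has its own resume condition, also without a taper. The skin row reads: "Resume study treatment if the rash improves to mild (localized) and the corticosteroid dose is <7.5 mg/day".
- **Table JZDA.7.4, footnote b.** If the toxicity has not come down to Grade 0-1, or the steroid to 10 mg/day prednisone equivalent or less, within 12 weeks, the site consults the sponsor about stopping.

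No sentence ranks these rules, and none says from which date a delay is counted.

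**The concern.** A site managing one irAE can find different restart conditions depending on which line it reads: Grade ≤1, a low residual steroid dose, or a completed taper. A month-long taper also sits against a 28-day delay limit, so following the taper sentence can by itself bring a patient to a discontinuation criterion.

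Safety and tolerability are the primary objective of both phases. Dose reductions are not permitted, so delay and discontinuation are the only modifications available. Section 7.2.2.3 names dose adjustments, including delays, among the inputs to the recommended Phase 2 dose (RP2D). SAP 5.12.1 and 5.12.3 summarise delays, dose intensity and discontinuations due to adverse events. If sites follow different sentences, those summaries partly measure the reading chosen rather than how the drug is tolerated. When patients are re-exposed after an irAE would also vary between sites. The route past 28 days requires clinical benefit and no progression, so continued exposure after a long delay would be tied to outcome.

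**Working it through.** The plan gives no figure to reproduce. The check compares the rules and then does calendar arithmetic.

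**1. The rules side by side**

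| Source | Restart when | Steroid status at restart |
|---|---|---|
| 7.4 text | Taper complete | Taper finished |
| Six steroid rows | Grade ≤1 | Not stated; the text has the taper starting here |
| Skin row | Rash mild | Still allowed, below 7.5 mg/day |
| Footnote b | Consult if not improved by 12 weeks | 10 mg/day or less is the threshold |

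The skin row and the taper sentence conflict on their face. In the six rows the table's trigger comes about one month before the text's.

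**2. Inputs for the timing**

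- Dosing interval 14 days (Table JZDA.7.1), so the next dose falls due on day 14 after the last.
- Delay limit 28 days (Sections 7.4 and 8.1).
- T, taper length: the text says 1 month; assumed 28 to 31 days.
- s, onset day after the last dose: not given; assumed 0 to 14.
- t, days from onset to Grade ≤1: not given; assumed 0 to 21.

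**3. Delay counted from the missed dose**

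Earliest restart is day s + t + T, so delay = s + t + T − 14. It stays within 28 days when s + t ≤ 42 − T:

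- T = 28: s + t ≤ 14
- T = 30: s + t ≤ 12
- T = 31: s + t ≤ 11

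With T = 30, onset on day 3 and t = 5 give 3 + 5 + 30 − 14 = 24 days, which fits. Onset on day 7 and t = 7 give 7 + 7 + 30 − 14 = 30 days, which does not.

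The table below gives the share of the 15 possible onset days (0 to 14, equally weighted for illustration only) on which the taper fits:

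| t | T = 28 | T = 30 | T = 31 |
|---|---|---|---|
| 3 | 12/15 = 80% | 10/15 = 67% | 9/15 = 60% |
| 7 | 8/15 = 53% | 6/15 = 40% | 5/15 = 33% |
| 10 | 5/15 = 33% | 3/15 = 20% | 2/15 = 13% |
| 14 | 1/15 = 7% | 0 | 0 |

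Over the full assumed range the share runs from 100% (T = 28, t = 0) to 0% (for example T = 31, t = 21).

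**4. Delay counted from onset, or event found on the due day (s = 14)**

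Delay = t + T. Even at t = 0 this is 30 days for T = 30 and 31 days for T = 31. Only T = 28 with t = 0 meets the limit.

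**5. Where the protocol itself narrows the slack**

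- Laboratory tests are scheduled no more than 3 days before an infusion (Table JZDA.2.1), so laboratory-defined events found at scheduled tests have s of about 11 to 14. Taking t = 3 to 14 and T = 28 to 31, delay runs from 11 + 3 + 28 − 14 = 28 to 14 + 14 + 31 − 14 = 45 days. Only the corner at 28 does not exceed the limit. Unscheduled tests could find events earlier.
- Gastrointestinal Grade 2 events receive prednisone only after more than 5 days, so t is at least 6. At T = 30, fitting then needs s ≤ 12 − 6 = 6.

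**6. Footnote b**

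12 weeks is 84 days, three times the 28-day limit, and its 10 mg/day threshold differs both from the skin row's and from a completed taper.

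**The case against.** There are five arguments on the other side.

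1. *The two-week interval gives slack.* This stands. A withheld dose is not late until day 14, so early events that settle quickly fit within 28 days. A reader might infer that a one-month taper can never fit; step 3 shows that it can.
2. *Section 8.1 carries an exception, and 7.4 provides a fallback to the first day of the next cycle.* Both are true, and a patient within the exception does not meet the criterion. But the exception is labelled rare and requires clinical benefit, which is a poor basis for a routine instruction.
3. *The rules can be read cumulatively: Grade ≤1 and taper complete.* This would reconcile the six rows, although the protocol does not say so. It leaves the skin row's dose threshold without a function. One could reply that a complete taper need not mean zero steroid, since Table JZDA.7.5 generally permits up to 10 mg/day prednisone equivalent during treatment. That would soften the skin conflict, but the text does not define completion that way.
4. *Many steroid-treated events are outside the conflict.* This stands. Several higher-grade rows discontinue outright, DLT-equivalent toxicities are a discontinuation criterion under 8.1, and some milder events may need no systemic steroid. Local guidelines may also replace the table, though 7.4 does not extend that to the taper sentence or the 8.1 limit, and it adds another source of variation between sites.
5. *Dose escalation is unaffected.* This largely stands. Escalation rests mainly on Cycle 1 DLTs, and no dose modification is allowed in Cycle 1. The effect is on later delays, discontinuations and dose intensity, and reaches the RP2D only as one input among several.

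**Conclusion.** Wrong as written, as an internal inconsistency. The taper sentence contradicts the skin row and does not match the resume trigger in six other steroid rows. Footnote b's consultation trigger is not aligned with either. A one-month taper uses most or all of the 28-day allowance. Counted from the missed dose, it fits only when onset day plus days to Grade ≤1 is at most about 11 to 14. Counted from onset, or for an event found on the due day, a taper of 30 days or more always exceeds the limit. Many resumable irAEs treated with systemic steroid would therefore depend on an exception meant to be rare.

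This rests on an assumed taper length of 28 to 31 days and on assumed onset and resolution times. Two stronger readings are not supported. A reader might infer that almost every steroid-treated irAE meets a discontinuation criterion; the documents give no timing data, so no share can be stated, and the exception and the outright-discontinuation rows limit the claim. A reader might also take footnote b as a further limit on delay; it only prompts a consultation. The effect on the tolerability summaries is indirect and is not quantified here.

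**What to change.** Amend Sections 7.4 and 8.1 and Table JZDA.7.4 so that they state one consistent restart condition and one maximum delay:

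- reconcile the taper sentence with every resume row, including skin and non-thyroid endocrine, and say whether the conditions are cumulative;
- define when a taper counts as complete;
- align footnote b with the delay limit, or say how the two relate;
- define the date from which a delay is counted (missed dose, onset or last dose), and use the same definition for the delay summaries under SAP 5.12.1;
- say whether a delay caused only by the required taper falls under the exception in 7.4.

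Which restart condition and which maximum delay apply is for the clinical team. The cost is protocol wording plus a one-line definition in the SAP. Sample size, assessments and analysis methods do not change.

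### Section 7.4 requires study drug to be withheld for a drug-related toxicity of any grade, but Table JZDA.7.4 says to continue for some related events, and nothing ranks the two

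*Protocol*

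**What the plan says.** Two current parts of Protocol Section 7.4 tell the investigator what to do with study drug when a related toxicity occurs.

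- **The running text.** "Study treatment must be withheld if the patient experiences a drug-related toxicity or a severe or life-threatening AE". The severity qualifier belongs to the second limb (the AE). The first limb, a drug-related toxicity, carries no grade, organ or duration limit and no reference to the tables.
- **Table JZDA.7.4.** Its title sets its scope: "Dose Modification Guidelines and AE Management for Toxicities At Least Possibly Related to Study Drug". For symptomatic thyroid issues it says "Start thyroid replacement therapy and/or medical management and continue study treatment", with a hold only at Grade 3 hyperthyroidism and discontinuation at Grade 4. For Grade 1 renal and urinary events the whole instruction is "Continue study treatment". For Grade 1 respiratory events it is "Consider withholding study treatment until the patient is stable".

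Section 7.4 also tells the investigator to judge relatedness and then apply the dose-modification guidelines. The only statement of precedence concerns local irAE guidelines, which supersede Table JZDA.7.4 where the investigator thinks fit. Nothing ranks the table against the sentence.

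Downstream, Section 7.2.2.3 lists among the inputs to the RP2D "dose adjustments (delays, reductions, or omissions), AEs, chronic intolerance, PK and pharmacodynamic data, and irAEs". Protocol Section 10.3.3.4 and SAP Section 5.12.1 summarize omissions, delays and dose intensity, and the SAP tabulates dose adjustments with their reasons for each cohort.

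**The concern.** For the same related event, one text makes a hold compulsory and the other says to keep dosing. A careful site or monitor could treat continued dosing after a symptomatic thyroid event as a deviation. Another, equally careful, could treat a hold as a departure from the table.

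Patients with the same event could therefore be managed differently. Tolerability is the primary objective in both phases, and a cohort's delays and dose intensity are meant to describe how the drug is tolerated. If sites follow different texts, those summaries partly describe the text followed. There is also a possible effect on staying on treatment: Section 8.1 discontinues a patient whose delay exceeds 28 days, apart from the exception in Section 7.4. A persistent low-grade related event could then count towards that limit under one reading and not under the other.

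**Working it through.** The plan states no figure to reproduce on this point. The check sets the texts side by side and then applies the SAP exposure formula to one example.

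**1. Do the texts cover the same events?** The table covers toxicities at least possibly related to study drug, and the sentence covers drug-related ones. Even if drug-related is read more narrowly than possibly related, an event judged clearly related falls under both.

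**2. What does each direct?**

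| Related event | Section 7.4 sentence | Table JZDA.7.4 | Relation |
|---|---|---|---|
| Thyroid, symptomatic, other than Grade 3–4 hyperthyroidism | Hold, mandatory | Continue | Opposite |
| Renal, Grade 1 | Hold, mandatory | Continue | Opposite |
| Respiratory, Grade 1 | Hold, mandatory | Hold optional | Weaker, not opposite |

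Table JZDA.7.3 adds a related case: "Patients who experience a Grade 3 IRR that resolves within 6 hours may continue on study treatment". That permits treatment after resolution, so it does not contradict the sentence as directly as the first two rows do. It still belongs in any reconciliation.

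**3. When can the conflict operate?** Section 7.4 allows no dose modification in the Phase 1a DLT observation period (Cycle 1). In Phase 1a the conflict therefore acts from Cycle 2 onwards. In Phase 1b it can act in any cycle.

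**4. What does it do to one patient's dose intensity?** Inputs:
- Formula (SAP Section 5.12.1): dose intensity = cumulative dose / exposure weeks, where exposure weeks = (last dose date − first dose date + 14)/7.
- Schedule (Protocol Table JZDA.7.1): every 2 weeks. The example uses 200 mg, the Cohort A5 dose.
- Assumptions: four doses, all eventually given (800 mg in total), and one thyroid or Grade 1 renal event that comes due for a decision at the Day 29 dose, after Cycle 1.

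| Action | Last dose | Exposure weeks | Dose intensity | Delays |
|---|---|---|---|---|
| Continue (table) | Day 43 | (43 − 1 + 14)/7 = 8 | 800/8 = 100 mg/week | 0 |
| 14-day hold (sentence) | Day 57 | (57 − 1 + 14)/7 = 10 | 800/10 = 80 mg/week | 1 |
| 28-day hold (sentence) | Day 71 | (71 − 1 + 14)/7 = 12 | 800/12 = 66.7 mg/week | 1 |

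Relative to continuing, the reduction is (100 − 80)/100 = 20% for the shorter hold and (100 − 66.7)/100 = 33% for the longer one. The event and the total dose are the same in every row.

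**5. Can this be scaled to a cohort?** Not from the documents, which give no rate for the events concerned. Not every such event would delay a dose either: with 14 days between infusions, one that resolves in between may cause no delay.

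**The case against.** The strongest reply is that there is no real conflict, only a general sentence made specific by a table. Section 7.4 instructs investigators to apply the dose-modification guidelines, the table carries that name and is introduced as giving criteria for delays and discontinuations, and the section also says that doses may be delayed. Many sites would read it so. This shows that a sensible reading exists, but not that the protocol requires it. The sentence is mandatory and unqualified, the table is introduced as guidance, and no text ranks one over the other.

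The reply does succeed against several stronger readings that a reader might infer:

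- **That the conflict runs through every cycle of both phases.** The ban on dose modification in Phase 1a Cycle 1 rules this out.
- **That footnote d, on lipase and amylase, is another contradiction.** It says that certain elevations "will not require discontinuation of LY3415244". Footnote b defines discontinuation as permanent, so a temporary hold remains compatible with it.
- **That a patient held under the sentence has no route back to treatment.** Section 7.4 gives general timing for resumption and conditions for longer delays. For irAEs that the table does not list, it sends the investigator to the sponsor's physician. The gap is confined to related non-immune toxicities outside the tables.
- **That the number of affected patients can be estimated by assuming a rate of related Grade 1 events.** That is a different set of events: the table itself holds or stops drug for some of them, such as Grade 1 pancreatitis and Grade 1 cardiac events.
- **That each hold means lost doses.** A delay may only shift doses, and the SAP lists delays separately from omissions.
- **That the RP2D turns on this.** Section 7.2.2.3 relies on the totality of the data, Section 7.2.2.1 makes safety data, DLTs in particular, the primary criteria for escalation, and no rule uses a delay rate as a threshold.

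**Conclusion.** The inconsistency stands. Two current instructions in Section 7.4 direct opposite study-drug actions for symptomatic thyroid issues and Grade 1 renal events, and differ in force for Grade 1 respiratory events. Sites can legitimately diverge, in Phase 1a after Cycle 1 and throughout Phase 1b.

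For one patient in the example, the choice of text changes the delay count from 0 to 1 and lowers dose intensity by 20% to 33%. Those figures rest on the assumed four doses, hold lengths and timing; they are not a forecast. The cohort-level effect is unknown. The consequence for the RP2D is indirect, through one of several inputs. The documents do not support saying that escalation decisions or the RP2D would be wrong. The case for correction rests on consistent patient handling and on delay and dose-intensity summaries that can be interpreted.

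**What to change.** Amend Section 7.4 so that the withholding sentence and Tables JZDA.7.3 and JZDA.7.4 agree, and state their order of precedence. The amendment should settle three things:

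1. Whether the sentence or the table entry decides the study-drug action when a related event appears in a table.
2. How the provision that local guidelines supersede Table JZDA.7.4 fits into that order.
3. What applies to related non-immune toxicities that the tables do not list.

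Which clinical rule to adopt is for the sponsor; the statistical need is only that one rule applies at all sites.

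The cost is a few sentences or table cells in a protocol amendment, with no extra patients or procedures. A new eCRF reason code would add little, because Section 7.4 already requires the rationale for each modification to be documented and SAP Section 5.12.1 already summarizes the reasons.
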